#### **6.4.3. Vital Signs**

Vital signs (temperature, height/length, and weight) are a part of the physical examination, which will be performed at the Screening visit and Month 3/ Final visit. All vital signs will be reported in metric units.

#### **6.4.4. Physical Examination**

Physical examinations will be done by a physician at the Screening visit and Month 3 /Final visit. The following sites will be examined: head, eyes, ears, nose, throat, neck, chest, lungs, heart, abdomen, skin, and lymph nodes; and the following systems will be assessed: musculoskeletal and neurological.

### **7. STATISTICAL METHODS**

#### **7.1. General Methodology**

For statistical analysis purposes, Baseline is defined as the last measurement prior to the first application of the study drug.

In general, no formal inferential analyses are planned for the Baseline and safety data, and only descriptive statistics will be provided.

For the descriptive statistics, the categorical variables will be summarized by frequency and percentage for each response category (number of patients, %) and the continuous variables will be summarized using means, medians, minimum, maximum, and standard deviations.

Data will be summarized by treatment groups, and overall (where appropriate).

## **7.2. Adjustments for Covariates**

Epidermolysis Bullosa (EB) type and Baseline characteristics of the target wound at Baseline, (ie., target wound size and target wound age) are considered to be potential effect modifiers. Their effects will be considered for the two primary efficacy endpoints (Month 3) as covariates.

Wound age is based on the wound start date provided by the subject from recall and as clarified in the NTF, it is calculated as follows: calculated wound age = Baseline date - wound start date. If the calculated wound age is  $\leq 365$  days then wound age used as a covariate in analysis is the calculated wound age. If the calculated wound age is  $> 365$  days, then the wound age used as covariate in analysis is replaced by 365 days. The reason for the definition is that it is difficult for the subject to provide an exact wound start date for old wounds.

Same covariates will be used in analysis of wound closure endpoints at other time points.

For other endpoints, EB type and the Baseline value for a given endpoint will be used.

## **7.3. Handling of Dropouts or Missing Data**

For the time to wound closure endpoint, data will be right censored at 3 months or at the time of patient's withdrawal from the study. For the second primary endpoint and for the binary secondary endpoints of wound closure, the first method of imputation for missing data will be Multiple Imputation (MI) using the Missing At Random (MAR) assumption. As clarified in the NTF, if the target wound closure occurred at a prior visit, the target wound is considered closed at all subsequent visits that took place. In such a case, no imputation is required for subsequent visits.

For the first MAR based multiple imputation, the MI procedure of the SAS® system will be used to generate sets of data with missing values imputed from observed data. It is expected that the pattern of missing data will be monotonic, with slight deviations being corrected by the Markov Chain Monte Carlo (MCMC) method of the MI procedure.

As per clarification in the NTF, after the MCMC correction, the rounding will be performed for the binary endpoint. If imputed values are greater than or equal to 0.5, the value is set to 1 and anything else is set to 0.

Linear regression will be employed to model the missing continuous data and a logistic regression model will be used for the binary data, with the following covariates included in the imputation model: treatment, EB type, Baseline characteristics of a given endpoint (as described in Section 7.2), and non-missing data from earlier time points. As per clarification in the NTF, if the Week 2 data for wound closure are missing, there are no previous visit data available to utilize in the imputation procedure. Therefore, patients with missing Week 2 wound closure data will be excluded from analysis. The imputed datasets will be analyzed using the methodology

described in Section 8. The results from the analysis of the multiple imputed datasets will be combined by the MIANALYZE procedure of the SAS system. The seed number to be used will be 010005 and the number of imputations is planned to be 5.

The final p-value, estimate of regression coefficient for treatment effect, and the 95% CI of the estimate of the treatment effect on each multiply-imputed dataset will be generated from the MIANALYZE procedure of SAS.

In addition, for the proportion of complete wound healing within Month 3, the final difference in proportions between treatment groups (SD-101-6% - Placebo) and the 95% CI of the final difference from each multiply imputed dataset will be generated using the method by Bohdana Ratitch et al. 2013.

To assess the robustness of the first missing data imputation result for the second primary endpoint, the following sensitivity analyses will also be conducted:

- a. The same multiple imputation method as above will be repeated but based on the Pattern-Mixture Model discussed by Bohdana Ratitch et al. 2013 under the Missing Not At Random (MNAR) assumption, by using the profiles from the placebo subjects with observed data to impute missing data
- b. Subjects with missing wound healing data within 3 months will be considered as ‘failures’ for the wound healing rate

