8.4. Withdrawal Criteria/Study Discontinuation

Patients may withdraw from the study at any time without stating a reason and without prejudice to further treatment. The Investigator may withdraw a patient from the study and discontinue study treatment and assessments at any time due to safety concerns or concerns about the patient's compliance with study requirements and procedures. Full skin examination will be performed at each visit. If SD-101 causes any significant rash that has not occurred previously in the patient, the Investigator should consider discontinuing the patient. In addition, if lesions appear to significantly worsen above the normal cycle seen in the patient, with use of SD-101, the Investigator should consider discontinuing the patient. If a patient discontinues treatment at any time after entering the study, the Investigator will make every effort to ensure the patient returns for all study visits.

Early discontinuation of any patient who has given informed consent/assent to participate will be recorded including the reason for discontinuation. The primary reason for a patient withdrawing prematurely will be selected from the following standard categories of early discontinuations.

1. Adverse Event (Adverse Reaction): Clinical events occurred or laboratory results are reported that in the medical judgment of the Investigator are grounds for discontinuation in the best interests of the patient.
2. Withdrawal of Consent: The patient desired to withdraw from further participation in the study. The patient is not obligated to provide any reason for withdrawal of consent, but where a reason is given this will be recorded on the eCRF.
3. Protocol Violation: The patient failed to adhere to the protocol requirements, at the Investigator's discretion.
4. Lost to Follow-Up: The patient stopped coming for visits and study personnel were unable to contact the patient.
5. Other: The patient was terminated for a reason other than those listed above, such as, termination of study by Sponsor or enrolled in the study by error when they did not meet inclusion/exclusion criteria.

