12.1. Estimated Sample Size

The primary efficacy endpoints for this study are the time to complete target wound closure within 3 months and the proportion of patients experiencing complete closure of their target wound within 3 months. These variables will be compared between SD-101-6.0 and SD-101-0.0 (placebo) via step-down testing to control type 1 error at overall level of 0.025 1-sided. Time to complete target wound closure is the first endpoint to be tested. Complete target wound closure is defined as skin re-epithelialization without drainage. The two treatment groups will be compared with respect to the primary endpoints using Cox Proportional Hazards model and Logistic Regression, respectively. Both models will be adjusted for covariates. For time to complete target wound closure, which is the first primary endpoint to be tested, the data will be right censored at 3 months or at the time of withdrawal from the study. If the first primary endpoint is significant, then the successful evidence of efficacy of SD-101-6.0 will be concluded and testing will proceed further to the second primary endpoint and then to the key secondary endpoints.

For the second primary endpoint and for relevant secondary endpoints, missing data will be imputed using Multiple Imputation (MI) method with the Missing At Random (MAR) assumption. Details will be described in the Statistical Analysis Plan.

To assess the robustness of the missing data, imputation methodology sensitivity analyses will also be conducted including an approach that subjects with missing wound healing data within month 3 will be considered ‘failures’ for the wound healing rate. Details will be provided in the Statistical Analysis Plan.

Assumptions underlying the sample size estimation are that 35% of placebo patients will experience complete closure of their target wound at or before the 3-month follow-up

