visit and at least 60% of patients treated with SD-101-6.0 will experience complete closure of their target wound by this time (hazard ratio approximately 2.127, assuming exponential hazards over time). Note that ALL wounds are open at baseline; hence, the survival endpoint is an open wound. It is expected that fewer wounds will stay open on test treatment than on placebo; hence, the expected proportions of open wounds at 3 months are 65% on placebo and 40% on test treatment, which corresponds to a HR=2.127. These yield the 35% expected wound closures for placebo (35% = 100% - 65% surviving open), and 60% for SD-101-6.0 (60% = 100% - 40% surviving open). Using these assumptions and a 1-sided overall alpha of 0.025, approximately 150 patients will be required (75 in each group) to provide at least 86% power for time to complete target wound closure. There is estimated 85% power for the proportion of patients with complete target wound closure.

Therefore, approximately 150 patients are to be enrolled.

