## **4. STUDY DESIGN**

### **4.1. General Design**

This is a Phase 3, multi-center, randomized, double-blind, placebo controlled study to assess the efficacy and safety of SD-101-6% cream vs. Placebo on lesions in approximately 150 patients with Simplex, Recessive Dystrophic, or Junctional non-Herlitz Epidermolysis Bullosa.

Patients will be randomized on a 1:1 basis to either SD-101-6% cream or Placebo cream. SD-101-6% or Placebo will be applied topically, once a day to the entire body for a period of 90 days.

Patients will have 1 target wound selected at Baseline by the investigator. The investigator should identify a target wound per the ARANZ SilhouetteStar™ system manuals and training provided. At screening, multiple wounds on the subject can be assessed against study inclusion/exclusion criteria. The selected target wound must be at least 21 days old (size 10 to 50 cm^2). Photographic confirmation of the target wound location will be collected at Baseline, and the picture saved from the first visit will be used to confirm location of the target wound at subsequent visits. Once the target wound is identified, it should be followed during the subsequent study visits 2, 3, 4, and 5. It should be ensured that only 1 wound (captured as wound A in the ARANZ system) is identified for the study.

Patients who have an eligible target wound and meet all other inclusion/exclusion criteria will be randomized. Patients who screen fail may be rescreened. The first dose of treatment will be administered during the office visit. Patients randomized will initially be given one-month supply of study drug.

The patient will return for scheduled visits in accordance with the protocol: Visit 2 (14 days ± 5 days from Baseline), Visit 3 (30 days ± 7 days from Baseline), Visit 4 (60 days ± 7 days from Baseline), and Visit 5 (90 days ± 7 days from Baseline) to have the target wound, previously identified at Baseline, re-assessed for the level of healing. In addition, itching, pain, body surface

area index (BSAI), and scarring of healed target wound will also be assessed at each visit. The ARANZ SilhouetteStar will be used to measure the target wound area at all visits.

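### The closure imputation model leaves out the wound area measured at every visit, so dropouts alike on baseline factors get the same imputed chance of closing whether their wound shrank or grew

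*SAP*

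**What the plan says.** SAP 7.3 imputes missing binary closure by logistic regression under MAR, with these predictors: "treatment, EB type, Baseline characteristics of a given endpoint (as described in Section 7.2), and non-missing data from earlier time points". SAP 7.2 identifies the baseline characteristics as target wound size and target wound age.

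Two places show what the earlier data are for closure. SAP 7.3 treats a patient whose Week 2 closure status is missing as having nothing from a previous visit to impute from, and excludes that patient. SAP 6.3.1 says the 3-month endpoint is imputed from values observed at previous visits. Post-baseline wound area is not named in either.

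SAP 7.3 also states that "if the target wound closure occurred at a prior visit, the target wound is considered closed at all subsequent visits that took place", and that such patients need no imputation. Under SAP 8.6.1.1, closure at any of the four post-baseline visits makes the patient a responder.

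The area data exist. SAP 4.1: "The ARANZ SilhouetteStar will be used to measure the target wound area at all visits". Amendment 1 adds a separate wound-size analysis (SAP 5.2), including a repeated-measures model on multiply imputed data (Table 14.2.18.2 in SAP 11.3).

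**The concern.** An imputation model under MAR should contain the measured variables that predict both the outcome and its absence. Here the only post-baseline predictor takes the same value for every dropout who needs a Month 3 value, so it cannot tell one from another. A wound nearly healed at the last visit and one that has doubled are treated alike if the patients match on treatment, baseline factors and last visit.

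Missingness could plausibly follow wound course. Protocol 8.4 asks the investigator to consider discontinuing a patient "if lesions appear to significantly worsen above the normal cycle seen in the patient". If patients with growing wounds leave and are not seen again, they are imputed as average open wounds. The endpoint affected is second in the testing order, and under SAP 7.5 no key secondary is formally tested unless it is significant.

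**Working it through.** **Inputs**, from Protocol 12.1:
- Test level: "Using these assumptions and a 1-sided overall alpha of 0.025".
- Placebo closure rate: "35% of placebo patients will experience complete closure of their target wound at or before the 3-month follow-up".
- Active closure rate: "at least 60% of patients treated with SD-101-6.0 will experience complete closure of their target wound by this time".
- Effect on the time scale: "hazard ratio approximately 2.127, assuming exponential hazards over time".
- Sample size: 75 patients per arm.

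Neither document gives a dropout rate or a wound-area trajectory. Both are assumptions below.

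**1. The plan's own figures.**
- Hazard ratio: ln 0.40 / ln 0.65 = 2.127. This agrees.
- Proportion endpoint, Wald test on the log odds ratio: log OR = ln(0.60/0.40) − ln(0.35/0.65) = 1.0245. SE = √[1/(75×0.35×0.65) + 1/(75×0.60×0.40)] = 0.338. Power = Φ(1.0245/0.338 − 1.96) = 85.8%. One-sided Fisher exact gives 85.4%. The stated figure is 85%.
- Time to closure: expected events 75×(0.35+0.60) = 71.25. Freedman's formula gives 86.0%. The stated figure is at least 86%.

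The planned power is not in dispute.

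**2. What can vary among dropouts who need a Month 3 value.** A patient closed at any observed visit is already a responder. Those left were open at every visit seen. Their imputed probability can differ only by treatment, EB type, baseline size, wound age and last visit attended. For gaps between attended visits, the MCMC step may also use later visits, so the statement is exact for dropout but not for every gap in the 1- and 2-month endpoints.

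**3. Separation.** By the carry-forward rule, closed earlier implies closed later without exception in the fitting data. That coefficient therefore has no finite maximum-likelihood value. SAP 8.6.1.1 has a rule for separation in the analysis model; SAP 7.3 has none for the imputation model. No harmful effect on the imputed values of open patients has been shown.

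**4. Imputed chance under the planning hazards.** For a patient last seen open at Day 30, P(closed by Day 90) = 1 − S(90)^(60/90).
- Placebo: 1 − 0.65^(2/3) = 0.250.
- Active: 1 − 0.40^(2/3) = 0.457.

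**5. Illustrative simulation.** It uses 150,000 patients per arm calibrated to 35%/60%, sequential logistic imputation with the SAP covariates (EB type left out), and assumed area trajectories and dropout. Every dropout is taken to have no final visit. Both models are fitted in patients still open, so the separation in step 3 plays no part. The true difference is 0.247.

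| Dropout pattern, nominal rate 10% | Needing imputation, placebo / active | Planned model | With last area |
|---|---|---|---|
| Unrelated to area | 9.1% / 8.3% | 0.245 | 0.247 |
| Growing wounds leave, both arms | 13.4% / 7.0% | 0.236 | 0.246 |
| Growing leave on placebo, random on active | 13.4% / 8.3% | 0.213 | 0.244 |
| Growing leave on placebo, shrinking on active | 13.4% / 14.0% | 0.176 | 0.244 |
| Random on placebo, growing leave on active | 9.1% / 7.0% | 0.268 | 0.248 |

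With area-dependent dropout, the planned model ranges over 0.211 to 0.259 at a nominal 5% and 0.117 to 0.287 at 20%. With area in the model, the difference stays within 0.240 to 0.250 in all scenarios.

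Among patients needing imputation, across all scenarios:
- Wounds at least halved truly closed in 59–79%. The planned model imputes 37–50%; with area, 52–76%.
- Wounds that had grown truly closed in 1–2%. The planned model imputes 30–45%; with area, 1–3%.

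**6. Scale.** The SE of the difference is √[(0.35×0.65 + 0.60×0.40)/75] = 0.079. At a nominal 10% dropout:
- One rule in both arms: 0.247 − 0.236 = 0.011, or 0.14 SE, against the drug.
- Opposite rules by arm: 0.247 − 0.176 = 0.071, or 0.90 SE, against the drug.
- Growth-driven exits on active only: 0.268 − 0.247 = 0.021, or 0.27 SE, for the drug.

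**The case against.** A reader might infer that patients withdrawn for worsening are routinely imputed as average wounds and that this inflates the drug's effect. The documents do not support that reading.

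- **Follow-up continues.** Protocol 8.4 and 8.5 ask for every effort to bring patients who stop treatment back for all visits. The schedule in Protocol 11 makes Visit 5 also the early-termination visit, with an ARANZ assessment. SAP 6.2.2, on its wording, takes a final visit before Day 76 as the Month 3 value, although its only example is a Day 46/Day 75 case. A withdrawn patient who attends that visit is observed, not imputed. This stands. It leaves mainly patients with no final visit, and the simulation above does not model it.
- **Direction is not fixed.** A bias in favour of the drug can be produced: with no treatment effect and growth-driven exits of 4% versus 10%, a separate simulation gives +2.4 points under the planned model and +0.1 with area. That imbalance is imposed. If the cream did nothing, growth-driven exits should be similar in the two blinded arms.
- **A safeguard is planned.** Missing-as-failure is pre-specified (SAP 7.3, 8.6.1.2, Table 3). It is nearly right for grown wounds, of which 1–2% closed. It is not right for shrinking ones, and the placebo-based MNAR analysis repeats the same imputation method, so it also lacks area.
- **The precision gain is small.** In the separate simulation, area cuts the imputation SD of the difference from about 2.0–2.2 to 0.9–1.1 points. Added in quadrature to 7.9 points, √(7.9² + 2.1²) = 8.2 becomes √(7.9² + 1.0²) = 8.0, a gain of 2–3%.
- **The wording is not exclusive.** SAP 7.3 does not expressly rule out area. Closure status is the natural reading of 6.3.1 and the Week 2 rule, but it is an inference. The SAP should name the variables.

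**Conclusion.** The point holds as a modelling weakness with conditional consequences. For dropouts needing Month 3 imputation, the planned model cannot distinguish shrinking from growing wounds among otherwise similar patients, and a strong predictor already collected goes unused.

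Any bias is near nil if missingness is unrelated to area. If missingness depends on area differently by arm, it can take either sign. The sizes above rest on assumed trajectories and dropout, and on every dropout lacking a final visit; the early-final-visit rule should make the real effect smaller. The weakness reaches the second primary endpoint and the binary closure secondaries. It does not touch the Cox analysis of time to closure, on which study success alone depends (SAP 7.5). The documents do not support a claim that the plan favours the drug.

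**What to change.** In SAP 7.3:
- Fit each visit's closure imputation model only among patients still open at the previous visit.
- Use treatment, EB type, baseline wound size, wound age and log ARANZ target wound area (or its log ratio to Baseline) at the last attended visit. Name these variables.
- Impute area sequentially where a later step needs it.
- Drop the earlier open/closed flags, which also removes the separation.
- Use the same predictor in the placebo-based MNAR analysis.

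No new data are needed, and the imputation model becomes only slightly more complex. SAP section 2 states that Amendment 1 includes changes made after database lock, so the new model should not replace the pre-specified one without saying so. If the primary method is frozen, report this as a labelled supportive analysis beside it, without confirmatory status.

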#### **7.4. Multi-center Studies and Pooling of Centers**

All study sites will be included in the statistical analyses. However sites will be pooled according to geographic regions (US, Europe, and Rest of the World [ROW]).

#### **7.5. Multiple Comparisons/Multiplicity**

The two primary efficacy endpoints for this study are time to complete target wound closure within 3 months and the proportion of patients experiencing complete closure of their target wound within 3 months. These variables will be compared between SD-101-6% and Placebo, and tested via a step-down procedure beginning with the time to complete target wound closure. This will address multiplicity and control overall type 1 error level at 0.05 2-sided. Note that if the first primary endpoint to be tested (time to complete wound closure within 3 months) meets the significance criterion of  $p < 0.05$  2-sided the study will be declared a success. If the first primary endpoint does not meet the significance criterion, the second primary endpoint (proportion of patients experiencing complete closure of the target wound within 3 months) will not be formally tested. Formal testing of the first key secondary endpoint at 0.05 2-sided will proceed (which is equivalent to 0.025 1-sided) if both primary endpoints are significant. If the first key secondary endpoint is statistically significant, then the second endpoint on the list of the key secondary endpoints will be tested at the two-sided 0.05 alpha level. Formal statistical testing will not proceed to the next endpoint if the current endpoint does not reach statistically significant level of 0.05 (two-sided). While the formal statistical testing will not proceed, nominal p-values will be generated for all endpoints.

Following the evaluation of the two primary endpoints, the ranking of the key secondary endpoints is as follows:

1. Proportion of patients experiencing complete closure of their target wound within 2 months
2. Proportion of patients experiencing complete closure of their target wound within 1 month
3. Change in lesional skin based on BSAI at Month 3, compared to Baseline
4. Change in Total Body Wound Burden at Month 3, compared to Baseline
5. Change in itching assessed at Day 7, compared to Baseline
6. Change in pain assessed at Day 7, compared to Baseline

The inclusion of other secondary endpoints listed in Section 6.3.3 is intended to yield supportive evidence related to the primary and key secondary objectives. Statistical tests of these variables are considered exploratory and no adjustment for multiplicity for these other secondary endpoints will be made.

